12.1.2 Sensitivity Analysis Method(s)

The rate of ML decline endpoint will also be analyzed as follows:

- Repeat primary analysis (T-test) on the PP population by removing any matched set where the Study 203 member is not within the PP population.
- Test difference in rate of ML decline using the Sign test (Binomial) for the ITT and PP populations. The slope for each matched Study 203 patient is compared to the average slope of the Study 901 patient(s) of the 3-1 matched set.
- Repeat primary analysis on the baseline ML<6 population and baseline ML=6 population.
- If not all Study 203 patients have at least one Study 901 match, produce summary statistics for the rate of ML decline for the ITT and matched Study 203 populations.

Analyses of other measures of ML change are outlined in the next subsections and are based on the ITT population with matching.

BIOMARIN	Statistical Analysis Plan BMN190-203	Page 24
-----------------	---	----------------

12.1.2.2 Time to Unreversed 2-point Decline or Score of Zero

Response defined as the absence of an unreversed two-point decline or score of zero in ML score by last assessment relative to baseline, will be analyzed using Kaplan-Meier methods and the Cox proportional hazards model. An unreversed two-point decline is defined as any decline of 2 points or more that had not reverted to a 1-point decline (or better) as of the last recorded observation. An unreversed score of zero is a score of zero that did not subsequently increase to a score greater than zero as of the last recorded observation.

The Cox model will include an indicator variable for study group and no additional covariates since the study groups are matched on the important variables. Kaplan-Meier curves will be produced for the two matched cohorts. Time from baseline to the first unreversed 1-point decline in ML score will also be displayed by Kaplan-Meier method. The Cox model and Kaplan-Meier curves will weight Study 901 patients according to the number of matches: weights 1/3, 1/2, 1 normalized to the number of Study 901 patients matched to Study 203 patients, for 3, 2, 1 matches respectively.

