Twenty-four subjects were enrolled in Study 190-201/190-202, 23 of whom constituted the efficacy population. Interim efficacy results demonstrated a statistically significant and durable treatment effect in attenuating disease progression as measured by CLN2 scores and in comparison to natural history. Of the 24 patients enrolled into Study190-201, all but 2 subjects were in the active loss of function phase of the disease characterized by both notable disease burden and decline by a median value of 2 points per 48 weeks. In the 23 subjects who received BMN 190 for at least 96 weeks in Study 190-201/ 190-202, the median time until a 2-point decline in the motor–language score was not reached and was 345 days for historical controls. The mean (SD) unadjusted rate of decline in the motor–language score per 48-week period was 0.27 (0.35) points in treated subjects and 2.12 (0.98) points in 42 historical controls (mean difference, 1.85; P < 0.001). Common AEs included convulsions, pyrexia, vomiting, hypersensitivity reactions, and failure of the intraventricular device. In 2 subjects, infections developed in the intraventricular device that was used to administer the infusion, which required antibiotic treatment and device replacement.

PK analysis of ICV-delivered BMN 190 demonstrates concentrations and exposures that are three orders of magnitude greater in the CSF than in the plasma.

No association was found between ADA, including drug-specific IgE positivity, and incidence or severity of hypersensitivity adverse events.

Taken together, the response in the treated group is significant when compared to the loss of function predicted by natural history studies. The conclusions of treatment effect are constant across all analysis methodologies and sensitivity analyses. Most patients (87%) experience neurodegenerative stabilization, in which active decline in function is either halted (57%), has an early single point decline with no subsequent loss (22%) or actually improves function on treatment (9%).

In conclusion, BMN 190 via ICV infusion is generally safe and well tolerated. BMN 190 treatment demonstrated a durable and clinically meaningful therapeutic effect on attenuating disease progression compared to natural history.

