3.2 Study Design

This is a Phase 2 open-label, multicenter study in pediatric patients < 18 years of age with CLN2 disease. The study is designed to assess disease progression in CLN2 patients treated with BMN 190 compared to natural history data from untreated historical controls (data from a CLN2 disease patient registry and data from siblings with CLN2 disease, when available). The comparison of treated subjects with untreated controls is from the time of the initiation of study drug.

The planned enrollment for this study is at least 10 subjects: at least 5 subjects with a Hamburg ML score \geq 5 points, at least 5 subjects with a ML score < 5 points, and at least 5 subjects < 2 years of age. Study eligibility and enrollment occur before (\leq 21 days) subjects are admitted to the hospital for surgical implantation of an ICV access device. The first infusion is administered at least 14 days from surgery to implant the ICV reservoir and no more than 28 days after surgery. The Baseline visit is to collect clinical scores and clinical laboratory parameters and is to be completed no more than 2 days before the first infusion.

BMN 190 are administered every 14 days from the date of the first infusion (\pm 3 days) for at least 144 weeks according to the subject's age. At study completion or early termination visit, subjects who have ICV device removal are required to have a device safety follow-up visit at 4 weeks (\pm 3 days) after ICV device removal. All subjects require a safety follow-up visit at 6 months (\pm 1 week) after last dose.

CLN2 assessments are scheduled every 4 weeks, study completion/early termination, and safety follow-up visits. Cranial MRI is assessed every 24 weeks and at study completion/early termination visit. Immunogenicity assessment is based on CSF and serum lab draws collected at baseline, every 12 weeks, study completion/early termination, and safety follow-up visits (serum only). PK assessment is based on CSF and serum lab draws every 24 weeks and at study completion/early termination visit.

	BMN 190-203 Statistical Analysis Plan, Version 2.0	Pg. 12 of 53
---	---	--------------

The safety and tolerability of treatment will be assessed by collection of adverse events, physical findings, vital signs, ECG, EEG, and clinical laboratory tests.

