4.6 Handling of Dropouts and Missing Data

Missing ML assessments for symptomatic patients (baseline ML < 6 points) will not have much impact on the assessment of the primary endpoint since the disease progression on ML score is close to linear, estimation of rate of decline in ML is reliable for follow-up periods of greater than 6 months and all subjects had been followed > 6 months. Impact of missing ML assessments for asymptomatic subjects (baseline ML = 6 points) is also expected to be low since the follow-up of matched Study 190-901 subjects is limited to the length of follow-up of the Study 190-203 subject matched. Additional analyses will be conducted as appropriate to evaluate the impact of the COVID-19 pandemic on the study conduct and results, especially for the treatment effect as estimated in the trial.

BIOMARIN®	BMN 190-203 Statistical Analysis Plan, Version 2.0	Pg. 17 of 53
------------------	---	--------------

Statistical models for time-to-event analyses accommodate variable follow-up arising from staggered accrual or early study discontinuation, using an assumption of missing at random.

The CLN2 assessment schedule for Study 190-901 is not regular and does not generally match CLN2 assessment frequency in Study 190-203. Summaries of CLN2 score over a window grid would have highly variable N which is difficult to interpret. For this reason, interpolation will be used. Summaries of matched Study 190-203 and Study 190-901 CLN2 data will be based on data that has been imputed to the Study 203 visit target, using linear interpolation between Study 190-901 subject visits. Details are provided in [Appendix 4](#).

Partial or missing dates for adverse events and medications will be imputed conservatively by assignment to the earliest and latest possible dates for start and stop dates, respectively.

Some patients only have year of birth recorded as permitted by the site Institutional Review Board. Age in integer months is provided at each visit for Denver assessment. For subjects with incomplete date of birth provided, the date of birth will be imputed by back-calculation of birth date from the date of Denver assessment: (date of Denver) – round ((age in months) x (365.25/12)). For subjects with multiple Denver assessments, the average of the imputed date of births is used.

BIOMARIN®	BMN 190-203 Statistical Analysis Plan, Version 2.0	Pg. 18 of 53
------------------	---	--------------

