13 EFFICACY EVALUATIONS

The efficacy analyses will be based on the ITT population. The PP population will be used for sensitivity analyses of the primary endpoint.

There will be two sets of efficacy analyses. The first set will be descriptive summaries of the Study 190-203 subjects at baseline and follow-up visits for all efficacy endpoints. The second set of analyses are for the CLN2 scales M, L, V, S, ML, MLV, and MLVS and based on matching Study 190-203 subjects to Study 190-901 historical controls. These will include descriptive summaries and statistical model results for treatment comparison to natural history. If natural history data are available on siblings with disease, data of sibling pairs will be presented in listings and graphical displays.

The primary efficacy endpoint is the rate of decline in the 0 to 6-point ML score and the primary analysis is based on matching with Study 190-901 subjects. All matched analyses will be based on a single matched set and the algorithm for matching has been prespecified prior to any matched analyses and is described in [Appendix 3](#). The matching will be a 3-1 matching of the Study 190-901 Evaluable population and the Study 190-203 ITT population. The matching criteria are:

- Equal ML score
- Age within 3 months
- Genome: equal number of common alleles (c.622C→T, c.509.1G→C)

For all matched analyses, Study 190-901 subjects will be weighted inversely to the number of Study 190-901 subjects matched to a given Study 190-203 subjects. The weights for 3, 2, and 1 Study 190-901 subject(s) matched to a given Study 190-203 subject will be 1/3, 1/2, and 1 respectively and the weights are normalized to the number of Study 190-901 subjects matched to Study 190-203 subjects.

To demonstrate comparability of the matched groups, summaries of the following variables will be produced for each group, with Study 190-901 subjects weighted according to number of matches.

- Age (years, continuous)
- Sex (Female/Male)
- Genome
- Site / Region
- M, L, ML, MLVS scale scores

	BMN 190-203 Statistical Analysis Plan, Version 2.0	Pg. 27 of 53
---	---	--------------

- Age of diagnosis (years)
- Age of first symptoms (years)

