13.1.2 Sensitivity Analysis Method(s)

The rate of ML decline endpoint will also be analyzed as follows:

- Repeat primary analysis (T-test) on the PP population by removing any matched set where the Study 190-203 member is not within the PP population.
- Test difference in rate of ML decline using the Sign test (Binomial) for the ITT and PP populations. The slope for each matched Study 190-203 patient is compared to the average slope of the Study 190-901 subject (s) of the 3-1 matched set.
- Repeat primary analysis on the baseline ML<6 population and baseline ML=6 population

	BMN 190-203 Statistical Analysis Plan, Version 2.0	Pg. 28 of 53
---	---	--------------

- If not all Study 190-203 subjects have at least one Study 190-901 match, produce summary statistics for the rate of ML decline for the ITT and matched Study 190-203 populations.
- Repeat primary analysis but without the use of weights (equal weighting)

Analyses of other measures of ML change are outlined in the next subsections and are based on the ITT population with matching.

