Appendix 3: Matching of Study 190-901 and Study 190-203 Subjects

The population for the primary analysis is based on the ITT population and a 3-1 matching algorithm. This matching algorithm is based on maximizing the number of Study 190-203 subjects matched to Study 190-901 subjects and satisfying several criteria (baseline ML score equal, genome: equal number of common alleles, baseline age close and no more than 3 months apart). The data of Study 190-901 subjects will be restricted and includes the assessment at the age of the match as the baseline assessment. Duration of follow-up is measured with respect to this baseline. Follow-up assessments up to the largest duration that is less than or equal to the full follow-up duration of the matched 190-203 subject are included for the matched analysis. If this derived duration of follow-up for the Study 190-901 subject is not of duration 6 months or greater, then matching at this age of assessment will not be considered. For Study 190-901, where the first assessment of ML has the value 6, backwards imputation of the value 6 to earlier ages is allowed.

Distance is defined as the absolute value of the difference in baseline age for the potential match. Study 190-203 subjects are paired off from first through last and there are potentially 14 matched pairs. No Study 190-901 subject is matched more than once. To maximize the number of matched pairs, and overall low mean squared distance, at each pairing:

- Identify the Study 190-203 subject who has not yet been matched and has the least potential Study 190-901 candidates for pairing based on the requirement for equal baseline ML score, equal number of common alleles and distance ≤ 3 . If greater than one Study 190-203 subject is identified, break the tie by considering the number of potential Study 190-901 candidates for matching based on the requirement of distance ≤ 2 . Potentially, there are still ties and repeat as needed using distance criteria based on thresholds ≤ 1 and ≤ 0 .

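### The supportive Cox model for ML decline omits disease stage because the groups are matched, so its pooled hazard ratio sits closer to 1 than the within-stage ratio if ML=6 and ML<6 children differ in untreated hazard

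*SAP*

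**What the plan says.** Current SAP 13.1.3 analyses time to an unreversed 2-point ML decline or a score of zero by Kaplan-Meier and Cox methods. The Cox model has an indicator for study group and "no additional covariates since the study groups are matched on the important variables". The superseded SAP of 25 June 2020, bound in the same file, has the same sentence in its section 12.1.2.2.

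The matching rule in Appendix 3 is "baseline ML score equal, genome: equal number of common alleles, baseline age close and no more than 3 months apart", with up to three controls per treated child, and "there are potentially 14 matched pairs". Entry ML runs from 3 to 6. SAP 3.2 asks for at least five subjects with ML of 5 or more, and then "at least 5 subjects with a ML score < 5 points, and at least 5 subjects < 2 years of age".

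The SAP treats ML=6 and ML<6 as different stages elsewhere. SAP 4.6 calls them asymptomatic and symptomatic, and SAP 14.1.5 splits convulsion events at this line. For the rate of decline, SAP 13.1.2 has "Repeat primary analysis on the baseline ML<6 population and baseline ML=6 population", and 13.4 repeats it. No such split is planned for the Cox model or the Kaplan-Meier curves in 13.1.3. Sections 13.1.4 and 13.1.6 inherit the method.

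**The concern.** The reason given for leaving stage out is balance at baseline. Balance deals with confounding. In a Cox model, a strong predictor of event time that is left out still matters when it is perfectly balanced, because the risk sets change composition over time. If untreated ML<6 children decline sooner than untreated ML=6 children, the ML<6 controls have events and drop out of the control risk set. Treated ML<6 children, if the drug works, stay in theirs. Later comparisons then set a higher-risk treated mix against a lower-risk control mix.

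Two things follow. The single reported HR describes neither stage, and it depends on the stage mix and length of follow-up. The usual standard error also ignores the balance that the matching created, so the test rejects too rarely.

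The documents give reason to expect a stage difference. Protocol section 7 puts typical symptom onset at ages 2 to 4, and some enrolled children are to be under 2. Appendix 3 also lets an ML of 6 be carried back to earlier ages for controls, which presumes a period before decline.

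**Working it through.** **Inputs from the documents.** There are 14 treated children and at most 3 × 14 = 42 controls (Appendix 3). Under full 3:1 matching the normalized weights all equal 1. Follow-up is at least 144 weeks, taken as 1009 days. Protocol 7.2 says the median time to a 2-point decline "was not reached and was 345 days for historical controls". The same section gives decline rates of 0.27 and 2.12 points per 48 weeks; 0.27/2.12 = 0.13 serves as a rough guide to effect size, since a ratio of slopes is not an HR. The plan states no power, event count or HR for this model (SAP 3.5), so there is no planned figure to reproduce.

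**Assumptions.** The ML<6 control hazard is λ = ln2/345 per day. The ML=6 hazard is r × λ with r = 0.5, 0.25 or 0.1, or else decline starts after a delay. About half the children are at ML=6 unless stated. The test is two-sided at 0.05, a level the SAP states only for the t-test.

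**Mechanism by hand.** Take r = 0.25, a within-stage HR of 0.20 and half at ML=6. At day d, with m = d/345, the event-free proportions are:
- controls: 0.5^m (ML<6) and 0.5^(0.25m) (ML=6)
- treated: 0.5^(0.2m) (ML<6) and 0.5^(0.05m) (ML=6)

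The mean hazard in each group, in units of λ, is the average of 1 and 0.25 weighted by these proportions, times 0.2 for the treated.

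| Day | ML=6 share, controls | ML=6 share, treated | Control hazard | Treated hazard | Ratio |
|---|---|---|---|---|---|
| 0 | 50% | 50% | 0.625 | 0.125 | 0.20 |
| 345 | 63% | 53% | 0.530 | 0.121 | 0.23 |
| 690 | 74% | 55% | 0.446 | 0.117 | 0.26 |
| 1009 | 82% | 58% | 0.385 | 0.114 | 0.30 |

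The true ratio is 0.20 in both stages throughout. A large simulated sample gives a pooled Cox HR of 0.24 for this case.

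**Simulation, lower ML=6 hazard** (exponential times, 14 v 42, half at ML=6, 3,000 trials per row). Each cell shows the SAP model v the model stratified by ML=6/<6.

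| r | True HR | Large-sample HR | Rejection rate |
|---|---|---|---|
| 0.5 | 0.10 | 0.11 v 0.10 | 99.2% v 99.3% |
| 0.25 | 0.10 | 0.12 v 0.10 | 96.6% v 98.4% |
| 0.1 | 0.10 | 0.14 v 0.10 | 89.0% v 96.9% |
| 0.5 | 0.30 | 0.32 v 0.30 | 74.4% v 77.6% |
| 0.25 | 0.30 | 0.35 v 0.30 | 57.7% v 69.7% |
| 0.1 | 0.30 | 0.39 v 0.30 | 37.5% v 63.0% |
| 0.5 | 1 | 1.00 v 1.00 | 5.2% v 6.0% |
| 0.25 | 1 | 1.01 v 1.00 | 3.1% v 6.0% |
| 0.1 | 1 | 1.00 v 1.01 | 0.8% v 6.3% |

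The power loss is 0.1 to 7.9 points at HR 0.10 and 3.2 to 25.5 points at HR 0.30. With no stage difference the two models agree. A variance clustered on matched set recovers part of the power (37.5% to 49% in the r = 0.1, HR 0.30 row) but not the shift in HR.

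**Simulation, delayed onset** (Weibull shape 2 with median 345 days; ML=6 children enter at 12-30 months and start to decline at 40±6 months; 5, 7 or 9 of 14 at ML=6). At 169 weeks, and including two other age/onset settings, HR 0.10 is reported as 0.15-0.20 and HR 0.30 as 0.38-0.47. In the setting described:
- HR 0.13 becomes 0.22-0.25.
- Power at HR 0.30 is 58-63% v 85-91%.
- Null rejection is 0.6-1.6% v 5.4-5.9%.

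At 144 weeks, power at HR 0.13 is 87-95% v 98-99%. A rerun at 144 weeks, with the effect acting on each child's hazard after onset (2,000 trials per case), gave 34-48% v 70-85% at HR 0.30, a loss of 36 to 39 points, with null rejection of 0.2-0.5%. At HR 0.13 with r = 0.1 and half at ML=6, the exponential model lost 14 points (78% v 92%), the worst case found at that effect.

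**The case against.** The strongest reply is that matching does what the SAP needs. It removes confounding by stage, the pooled HR is a legitimate marginal quantity, and under no effect it is 1 with rejection at or below about 5%. The error cannot create a false claim of benefit. The analysis is supportive, no power was planned, and the primary t-test on slope is already repeated by stage. All of that stands. It limits how much this matters, but it does not make the stated reason correct.

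A reader might go further in four ways that the documents do not support.
- **That 345 days is the median for untreated ML<6 children.** Protocol 7.2 gives it for all the earlier study's historical controls, and that study's treated patients could enter at any ML of 3 or more, including 6. Its use here for ML<6 is an assumption.
- **That ML=6 children are infants on a plateau of a year or more.** The documents give neither the ages, number nor untreated hazard of ML=6 children. The age quota concerns those under 2, whatever their score.
- **That the lost power is large.** At a ratio near 0.13 it is mostly small to moderate. It is large only for clearly weaker effects.
- **That an ML=6/<6 stratum suits every time-to-event analysis.** This was not computed for time to zero or for the M and L scales, where distance to the event depends on the exact score.

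**Conclusion.** The point holds in direction. If untreated hazards differ by stage and the drug works, the SAP 13.1.3 HR is closer to 1 than the within-stage HR, and its test is conservative.

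The size rests on assumed ML=6 shares and hazards. A within-stage HR of 0.10 is reported as about 0.11-0.14 with a lower ML=6 hazard, and as about 0.15-0.20 with delayed onset. Null rejection falls to about 0.1-3%, except that it stays near 5% when the ML=6 hazard is half that of ML<6. The power loss near a ratio of 0.13 is about 0-11 points, beyond that only in the most extreme case tried. At HR 0.3 it is about 10-40 points, or about 3 when the ML=6 hazard is half. These figures assume full 3:1 matching, whereas the SAP allows three, two, one or no controls per child.

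The likely harm is an understated benefit in a supportive result. The primary slope conclusion does not change.

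**What to change.** In SAP 13.1.3, stratify the Cox model and its test by baseline ML (6 versus <6), the split already used in 13.1.2 and 13.4. Keep study group as the only covariate and keep the control weights. Show the Kaplan-Meier curves overall and by stage. Delete the clause saying that matching makes covariates unnecessary.

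Where 13.1.4 and 13.1.6 inherit the model, stratify by a baseline grouping suited to the endpoint, for example the baseline subscale score for M and for L.

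Matched ML analyses have already been produced on interim data (SAP 3.6.1), so record the date of and reason for the change, and report the unstratified HR alongside.

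The cost is SAP wording, one stratum term and two extra curve panels. The downsides are a small loss of information from two strata, an HR that is conditional on stage, and null rejection slightly above 5% (about 5-6% in these runs). Differences within a stage remain, so some shift may persist. Stratifying by matched set instead would cost more power (81% v 88% at HR 0.20 and r = 0.25).

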12.1.2.3 Summary by Visit

Summary statistics of ML score (continuous variable) and change from baseline at each windowed visit will be produced. A tabulation of ML score (categorical variable) and change from baseline at Weeks 48, 96, 144, and last assessment will also be provided.

For comparison with Study 901, to enable a descriptive assessment of ML scores at common time points where all subjects contribute to the descriptive statistics, each subject of the matching cohorts will have their ML scores imputed to those time points using linear interpolation. The time points for interpolation will be in accord with the Study 203 schedule of CLN2 assessments. [Appendix 4](#) describes the imputation procedure in greater detail. Summary statistics of interpolated values and change from baseline by visit will be produced for the matched groups. A graph of mean change from baseline and standard error by visit will be produced.

